### 4.2. Handling of missing data

Partially missing data (e.g. a missing Tinetti-Assesment) would be left out in the specific calculation, but data for the other Endpoints would be used, if complete. If there would be no complete sets of data for any Endpoint the data set would be discarded. Reasons for missing measurements will be stated in the publication.

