## 2 PROJECT OBJECTIVES AND DESIGN

### 2.1 Hypothesis and primary objective

Our broad objective is to prospectively examine in a prospective study whether an association exists between hyponatremia and psychomotor deficits. The specific aims are:

- A) To measure muscle strength by use of a dynamometer in patients presenting with moderate to severe hyponatremia (serum sodium  $\leq 125$  mmol/L) at the emergency department before and after correction of hyponatremia (serum sodium  $\geq 135$  mmol/L).
- B) To test for balance and gait disorders before and after correction of hyponatremia
- C) To investigate whether presence of hyponatremia is associated with cognitive impairment that is reversible after correction of serum sodium.

Our hypothesis is that hyponatremia is associated with reduced muscle strength, impaired balance, and cognitive impairment, and that the correction of the serum sodium will lead to an improvement of these parameters.

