### 2.2 Primary and secondary endpoints

- A) Muscle strength in pounds and kilogram before and after correction of hyponatremia.
- B) Results for the Tinetti performance-oriented mobility assessment (POMA) to evaluate static and dynamic balance abilities during and after correction of hyponatremia.
- C) Results for the Montreal Cognitive Assessment (MOCA) test to assess mild cognitive impairment before and after correction of hyponatremia.

Muscle strength at handgrip will be measured at time of presentation at our clinic with a serum sodium  $\leq 125$  mmol/L and 24 to 48 hours after correction of hyponatremia at a serum sodium  $\geq 135$  mmol/L using the Jamar® hydraulic hand dynamometer, Lafayette Instrument, Lafayette, IN, USA. Strength will be measured in pounds and kilograms thrice at baseline and after correction of hyponatremia, respectively. The best result of each test will be used for the analysis. The test will be conducted by either Drs. [name] or [name].

The Tinetti POMA, a simple, easily administered test, will be used to measure patients' gait and balance taking about 10 to 15 minutes [19]. Scoring of the Tinetti Assessment Tool is done on a three point ordinal scale with a range of 0 to 2. A score of 0 represents the most severe impairment, while a 2 would represent patient independence. The individual scores are then combined to form three measures; an overall gait assessment score, an overall balance assessment score, and a gait and balance score. The test has been validated in several studies and found to be a useful screening tool for gait instabilities and prediction of falls [20-22]. The Tinetti POMA form is shown in the Appendix. The test will be performed at baseline and 24 to 48 hours after correction of hyponatremia. The test will be conducted by either Drs. [name] and [name].

The MOCA is a 30-point test administered in about 10 minutes designed to identify mild cognitive impairment [23]. The test is validated for a large variety of diseases ranging from frontotemporal dementia to HIV or chronic obstructive pulmonary disease [24-27]. The MOCA form is shown in the Appendix. The test will be performed at baseline and 24 to 48 hours after correction of hyponatremia. The test will be conducted by either Drs. [name] and [name].

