### 3.4 Withdrawal and discontinuation

Patients are excluded from the project in case of withdrawal of informed consent. Endpoint-specific datasets will be included if complete (see Section 4.2.). Additional patients will be enrolled to compensate for drop-outs. Since the blood samples used are part of clinical routine no further steps are taken, the blood samples will be handled according to usual clinical routine.

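### Does leaving out incomplete tests whatever the reason bias the before-after comparisons, given that the protocol does not say how to score a test the patient could not do?

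*Protocol*

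**What the plan says.** Section 4.2 sets the rule for each endpoint separately: "Partially missing data (e.g. a missing Tinetti-Assesment) would be left out in the specific calculation". The patient's other endpoints are kept if complete. For a patient with nothing usable, "If there would be no complete sets of data for any Endpoint the data set would be discarded". On reasons, the only commitment is "Reasons for missing measurements will be stated in the publication".

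Section 3.4 agrees: "Endpoint-specific datasets will be included if complete (see Section 4.2"). It adds that drop-outs will be replaced.

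Section 2.2 describes the three measures. For the Tinetti items, "A score of 0 represents the most severe impairment". Grip strength is read three times at each visit, and "The best result of each test will be used for the analysis". On the third measure it says "The MOCA is a 30-point test administered in about 10 minutes". It places the Tinetti and MOCA forms in an appendix; only Appendix 1, the schedule of assessments, is in the text supplied.

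Section 4.1 compares the two visits with the Wilcoxon signed-rank test, which needs both values. Sections 3.1 and 6.1 restrict enrolment to patients who can consent for themselves.

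**The concern.** All three endpoints are performance tests of functions that the study expects low sodium to impair. Section 2.1 says so: "Our hypothesis is that hyponatremia is associated with reduced muscle strength, impaired balance, and cognitive impairment". A patient too weak to stand for the Tinetti assessment, or too slow to finish the MOCA, is therefore not missing at random; inability is itself an extreme value of the outcome.

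If such a test is recorded as missing, section 4.2 removes the pair. Removing patients who could not perform at baseline takes out those with most room to improve and can hide a real improvement. Removing patients who could not perform after correction takes out those who did worst and can create or inflate one. Replacing drop-outs restores the number of patients but not the kind that was lost. Publishing the reasons shows readers the selection without showing whether the result depends on it. Two assessors could also record the same non-ambulant patient differently, one as a score of 0 and the other as a blank, and section 4.2 would keep one pair and delete the other.

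**Working it through.** The protocol has no figure of its own on this point to reproduce, so the check has two parts.

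**Part 1: which reading does the text support?**

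- *Tinetti.* Zero is the anchor for the worst impairment. This is an item score, so it does not fully settle an assessment that was never started, but it gives inability a place on the scale.
- *Grip.* The best of three dynamometer readings is used; a patient who cannot squeeze can be recorded as 0.
- *MOCA.* A 30-point scale leaves room for very low scores.
- *Section 4.2.* It speaks of missing data and does not say that a failed test is missing.

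Where inability is scored, the pair is complete and section 4.2 does not touch it.

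**Part 2: if inability were treated as missing, how much could it matter?**

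Take N = 50 pairs (planned enrolment, section 3.1). Let kb patients be unable only at baseline and ka only after correction, leaving n = 50 − kb − ka complete pairs with standardised signed-rank statistic z_c. Compare the complete-pair p-value with the one obtained when the deleted pairs are put back with the most extreme ranks (largest improvement if unable at baseline, largest worsening if unable after correction). This bounds how far the two rules can differ; it does not estimate bias.

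- E(n) = n(n+1)/4 and S(n) = √[n(n+1)(2n+1)/24], so E(50) = 637.5 and S(50) = 103.6.
- W = E(n) + z_c·S(n) + kb·r, with r the mean of the top kb + ka ranks.
- z = (W − 637.5)/103.6.

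*Complete-pair results chosen mostly near the 0.05 boundary* (z_c is an assumption):

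| Unable at baseline | Unable after | Complete-pair p | Worst-rank p |
|---|---|---|---|
| 2 | 0 | 0.10 | 0.043 |
| 5 | 0 | 0.30 | 0.041 |
| 0 | 1 | 0.05 | 0.097 |
| 0 | 2 | 0.01 | 0.052 |
| 0 | 5 | 0.05 | 0.60 |
| 4 | 1 | 0.10 | 0.036 |
| 3 | 2 | 0.05 | 0.056 |
| 5 | 5 | 0.05 | 0.16 |

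Example, first row: W = 588 + 1.645 × 97.5 + 2 × 49.5 = 847.4; z = (847.4 − 637.5)/103.6 = 2.03; p = 0.043.

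*Complete-pair result at the level the design aims for.* Section 3.1 plans 90% power at two-sided 0.05 for the MOCA, so the expected statistic is z_c = 1.96 + 1.28 = 3.24 (p = 0.0012):

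| Unable at baseline | Unable after | W | z | Worst-rank p |
|---|---|---|---|---|
| 0 | 1 | 612.5 + 3.24 × 100.53 = 938.2 | 2.90 | 0.004 |
| 0 | 2 | 588 + 3.24 × 97.50 = 903.9 | 2.57 | 0.010 |
| 0 | 3 | 564 + 3.24 × 94.50 = 870.2 | 2.25 | 0.025 |
| 0 | 4 | 540.5 + 3.24 × 91.53 = 837.1 | 1.93 | 0.054 |
| 2 | 0 | 588 + 3.24 × 97.50 + 99 = 1002.9 | 3.53 | 0.0004 |

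Inability at baseline, the direction the hypothesis predicts, only strengthens the result. Three patients unable solely after correction leave it significant.

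*Simulated bias under assumed inputs* (mean 18, SD 6, correlation 0.6, n = 50, anyone below the baseline 15th percentile deleted):

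| Deleted if unable at | Mean change when truth is 0 | Mean change when truth is 2.0 | Two-sided rejection when truth is 0 |
|---|---|---|---|
| neither visit | 0 | 2.0 | 5.3% |
| baseline only | −0.65 | 1.35 | 11.5% |
| second visit only | +0.66 | 2.41 | 12.8% |
| either visit | about 0 | 1.70 | 4.7% |

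The mechanism is real and its sign depends on the visit. When the same threshold applies at both visits it cancels under no change and understates a true improvement.

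**The case for a change.** The strongest case for a change is that this is not simply left to an unseen analysis plan. The protocol's own statistics chapter fixes deletion whatever the reason, gives a missing Tinetti assessment as its example (the test a non-ambulant patient is most likely to be unable to do), and enrols patients with sodium of 125 mmol/L or below. A blank on the form may not be recoverable later as an inability, so the coding has to be right when the test is due. The remedy looks cheap: a field on the CRF, a scoring sentence, and a worst-rank sensitivity analysis per endpoint.

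Much of this stands. The rule ignores reasons, the visible text is silent on inability, and deletion would select on the outcome if inability were coded as missing. The figure of 3.24 is also only an expected value for the MOCA; an actual result may fall closer to the boundary, where one or two one-sided cases can change the conclusion, and grip and Tinetti have no power statement.

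Three things weaken it. The harm needs a chain of conditions, none with a rate in the protocol: a consenting patient is unable, the inability is recorded as missing rather than scored, cases fall mainly at one visit, and the result is borderline if they are few. The stated analysis is not itself wrong, since complete pairs would remain the natural primary analysis under any sensible refinement. And the remedy has costs. A test scored at the bottom counts as done and so enters the primary analysis, which means a grip test prevented by an unrelated illness could be recorded there as 0. If all three tests can be bottom-scored, the worst-rank analyses have few or no pairs left to add.

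**Conclusion.** No change to the plan is called for. Following section 4.2 as written is not shown to give a wrong result. The gap is a scoring convention of the kind that a test form, CRF or analysis plan settles, and the scales in section 2.2 lean towards scoring inability, in which case the problem disappears.

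The size and direction of any effect cannot be found from the documents. The illustrations rest on assumed numbers of unable patients, assumed complete-pair results and extreme ranks. Within them, inability at baseline works against the study's hypothesis, nearly balanced inability matters little, and at the planned 90% power it takes four patients in 50 unable only after correction to lose significance (p = 0.054).

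If the forms turn out to be silent, the investigators could note, as an optional clarification, that inability due to the impairment being measured takes the lowest score, that tests not done for other reasons (including unrelated illness) are missing, and that counts are reported by visit and reason. The commitment to publish reasons already covers most of the last item. The p-values above do not justify additional worst-rank analyses.

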## 5 REGULATORY ASPECTS AND SAFETY

### 5.1 Local regulations / Declaration of Helsinki

This research project will be conducted in accordance with the protocol, the Declaration of Helsinki [32], the principles of Good Clinical Practice, the Human Research Act (HRA) and the Human Research Ordinance (HRO) [30] as well as other locally relevant regulations. The Project Leader acknowledges his responsibilities as both the Project Leader and the Sponsor.

### 5.2 Notification of safety and protective measures (HRO Art. 20)

The project leader is promptly notified (within 24 hours) if immediate safety and protective measures have to be taken during the conduct of the research project. The Ethics Committee will be notified via BASEC of these measures and of the circumstances necessitating them within 7 days.

### 5.3 Serious events (HRO Art. 21)

If a serious event occurs, the research project will be interrupted and the Ethics Committee notified on the circumstances via BASEC within 7 days according to HRO Art. 21.

---

1 A serious event is defined as any adverse event where it cannot be excluded, that the event is attributable to the sampling of biological material or the collection of health-related personal data, and which:

- requires inpatient treatment not envisaged in the protocol or extends a current hospital stay;
- results in permanent or significant incapacity or disability; or
- is life-threatening or results in death.

#### **5.4 Procedure for investigations involving radiation sources**

This Study does not involve radiation sources.

#### **5.5 Amendments**

Substantial changes to the project set-up, the protocol and relevant project documents will be submitted to the Ethics Committee for approval according to HRO Art. 18 before implementation. Exceptions are measures that have to be taken immediately in order to protect the participants.

#### **5.6 End of project**

Upon project termination, the Ethics Committee is notified within 90 days. All health-related data are anonymized upon termination of data analysis.

#### **5.7 Insurance**

In the event of project-related damage or injuries, the liability of the Bürgerspital Solothurn provides compensation, except for claims that arise from misconduct or gross negligence.

### **6 FURTHER ASPECTS**

#### **6.1 Overall ethical considerations**

This is a prospective, observational study. No invasive interventions will take place and thus, there is no potential harm for the patients. Laboratory parameters will be re-ordered from blood samples already taken as a part of clinical routine, so no additional blood drawings are necessary for study purposes. Only patients who are able to give informed consent by themselves will be included in the study. There will be no compensation for the patients, neither monetary nor in another way.

#### **6.2 Risk-Benefit Assessment**

Hyponatremia is a commonly encountered problem in hospitalized patients and is associated with significant morbidity and mortality [1, 2, 10]. The present study could give more insight into the impact of this electrolyte disorder on important body functions, such as muscle strength, gait and balance, and cognition. If hyponatremia is associated with these conditions, specific preventive measures could be taken to avoid complications, such as falls and fractures, which are associated with significant mortality, morbidity, and a socioeconomic burden [18]. Additionally, if the negative influence of hyponatremia on psychomotoricity was shown, it could help increase physicians' awareness to correct hyponatremia and eliminate predisposing factors for this condition [17]. Since it is an observational study no specific risks are expected.

#### **6.3 Rationale for the inclusion of vulnerable participants**

Vulnerable Participants are not included in the Study.

### **7 QUALITY CONTROL AND DATA PROTECTION**

#### **7.1 Quality measures**

All data handling will be undertaken directly by the investigators. For quality assurance the Ethics Committee may visit the research sites. Direct access to the source data and all project related files and documents must be granted on such occasions.

## 7.2 Data recording and source data

Data will be collected on paper CRFs and transferred to a Microsoft Excel file by the investigators. The Paper CRFs will be subsequently stored in a lockable bin. The Excel file will be stored on a dedicated drive accessible only by the study team. The dedicated drive is part of the Hospital IT Structure and thus subject to data backup procedures.

## 7.3 Confidentiality and coding

**Project data** will be handled with uttermost discretion and is only accessible to authorized personnel who require the data to fulfil their duties within the scope of the research project. On the CRFs and other project specific documents, participants are only identified by a unique participant number. The Code will not include any parts able to identify a subject like name or date of birth.

All patient data will be stored in a lockable bin in an office room at the General Hospital Solothurn. Patient data will be entered into a Microsoft Excel database, Microsoft Corporation, Redmond, WA, USA, and stored electronically on a password-protected computer. Electronic patient data will be encrypted and only the investigators (Drs. [name] and [name]) will be able to identify patients by use of a personal identification number for every patient enrolled in the study. Data will be published anonymously.

## 7.4 Retention and destruction of study data and biological material

Health related data are stored for 10 years after publication of the research project. The blood samples are part of clinical routine and will be handled according to clinical routine. No blood samples will be stored for study purposes.

## 8 FUNDING / PUBLICATION / DECLARATION OF INTEREST

There is no funding for the project. The Investigators declare no conflict of interest.

## Appendix 1: Schedule of assessments

Time	0	Corrected sodium
Visit	Screening/1 st visit	2 nd visit
oral and written Information	+	
Written consent	+	
check inclusion-/ exclusion criteria	+	
Medical history	+	
Participant Characteristics	+	
Serum sodium measurements	+	+
MOCA	+	+
Tinetti Assessment	+	+
Grip Strength	+	+
